## 2. BACKGROUND

### 2.1.1 Study Agent

#### 2.1.1.1 PI3K Inhibitor Idelalisib

Idelalisib is a potent competitive inhibitor of the ATP binding site of the PI3K p110-delta catalytic domain, which is prominently expressed in cells of hematopoietic origin. Idelalisib is being developed by Gilead Sciences, Inc. as an anti-cancer agent for the treatment of solid and hematologic malignancies. *In vitro*, idelalisib is highly selective for the p110-delta subunit with an IC50 of 2.5 nM. In contrast, the IC50 for the alpha, beta and gamma subunits are 820,

565 and 89 nM, respectively. Idelalisib also showed a greater selectivity for mTOR and other related kinases, but no activity was seen against a panel of >400 diverse kinases (Lannutti 2011). Additionally, in cell-based assays, idelalisib showed a 240- to 2500-fold specificity for p110-delta than for other PI3K class I subunits.

### 2.1.5. Clinical experience with idelalisib

A total of 25 Phase 1, 2 and 3 clinical studies have been conducted in 300 healthy or non-hematologic subjects and 778 subjects with hematologic malignancies. Eleven studies have been completed in healthy or non-hematologic subjects to study the clinical pharmacology of idelalisib. These studies included phase 1 randomized placebo controlled dose escalation studies in healthy subjects and in subjects with allergic rhinitis, a phase 1 three-period crossover study, a phase 1 comparison study between capsules and tablets, a phase 1 mass balance study, phase 1 studies in patients with hepatic and renal dysfunction, a phase 1 randomized study to evaluate QT/QTc interval, a phase 1 bridging study that included Japanese and Caucasian subjects, a phase 1 to evaluate the effect of idelalisib on probe substrates (patients were on digoxin, midazolam and rosuvastatin), and a phase 1 open label study of idelalisib in combination with GS-9973.

Eight phase 1 and 2 studies have been undertaken in subjects with hematologic malignancies. These include a phase 1 sequential dose-escalation study (101-02), an open-label phase 1 in combination with chemotherapeutic agents and anti-CD20 monoclonal antibody therapy (101-07), a phase 2 study in combination with rituximab in elderly patients with CLL/SLL (101-08), a phase 2 in indolent NHL refractory to rituximab and alkylating agents (101-09), a phase 1/2 in previously treated indolent NHL (101-10), a phase 2 study in relapsed/refractory Hodgkin lymphoma (101-11), a phase 1/2 extension study (101-99) and a phase 2 study of idelalisib in combination with GS-9973 in relapsed/refractory hematologic malignancies (GS-US-339-0103).

In March 2016, decreased overall survival and increased rates of serious adverse events were observed in phase 3 studies evaluating the addition of idelalisib to standard therapies in first line CLL and relapsed iNHL. The excess deaths occurring among idelalisib-treated subjects were generally due to a higher rate of infectious events including sepsis, febrile neutropenia, and opportunistic infections such as Pneumocystis jiroveci (PJP) and cytomegalovirus (CMV). It was concluded that the increased risk of early death may not be outweighed by a reduced hazard of death from disease progression. Gilead conducted a review of its open phase 3 studies in the relapsed CLL setting, and there was no increased risk of death among subjects receiving idelalisib compared to the control groups. It was recommended that studies evaluating idelalisib in first line CLL or iNHL be terminated, and that monitoring inclusive of PJP, CMV and CBC monitoring. It has been further noted that severe hepatotoxicity occurs primarily in younger patients treated with idelalisib in the front line setting. The median time to onset of hepatotoxicity was 28 days.

### 2.1.6. Summary of Safety Data from Monotherapy Trials

On studies 101-02 (parent) and 101-99 (extension), no DLT was observed during the dose-escalation phase at doses of 50, 100, 200 and 350 mg PO BID, respectively. Therefore, an MTD was not reached. PK data showed no exposure differences between the cohort of patients who received 200 mg PO BID and 350 mg PO BID. Grade 3 or higher LFT elevations that occurred in 28 patients were transient and reversible, and not dose limiting, as they did not recur in 9 of the 14 (64%) patients who were re-challenged with idelalisib. During the 48-week study, the most frequent AEs of any grade were fatigue, diarrhea, pyrexia, nausea, rash, AST increase, cough and ALT increase. SAEs occurred in 44% of patients; the most frequent were pneumonia, febrile neutropenia, diarrhea, pulmonary embolism and acute renal failure. A total of 23 patients (12%) discontinued treatment due to AEs; the most frequent AEs were AST elevation and pneumonia. Twenty subjects (11%) died; 5 due to disease progression, 3 subjects from pneumonia and 12 attributed to fungal pneumonia, PJP, fungal sinusitis, acute respiratory distress, hypoxic respiratory failure, multi-organ failure, cardiac arrest, infection with neutropenia, septic shock and refractory MM. AEs leading to death were reported in 9/20 subjects. Of these, 3 were assessed as possibly related to idelalisib: pneumonia, fungal pneumonia and PJP.

On study 101-09 (indolent NHL), out of 125 participants, 108 and 86 subjects have been exposed to idelalisib 150 mg PO BID for >2 months and >4 months, respectively. Thirty seven percent had reductions to 100 mg PO BID or 75 mg PO BID during the study. Of 125 subjects, 123 (98%) reported an AE. The most frequent were diarrhea, fatigue, cough, neutropenia, nausea and pyrexia. Eighty-three subjects (66%) reported grade 3 or higher AE. The most frequent were neutropenia, diarrhea, increased ALT, pneumonia and increased AST. Twenty-two deaths (18%) were reported; 7 subjects (6%) experienced AES leading to death. AEs leading to death were ARDS, cardiomyopathy with cardiac

arrest, hypoxic respiratory failure and multi-organ failure, pneumonia, septic shock, toxoplasmosis and splenic infarction. Fifty-four patients (43%) experienced SAEs: diarrhea, pyrexia and pneumonia. A total of 19 patients (15%) discontinued the study due to AEs. Diarrhea, ALT and AST elevation, colitis and pneumonitis were the most frequently reported.

On the 101-10 study (low-grade NHL), exposure to drug ranged from 1 day to >6 months with a median of 3.6 months. One subject (9%) died due to GI bleed and sepsis, which the investigator considered not related to study drug. Ten patients (91%) reported at least 1 AE; 5 patients (46%) had grade 3 or higher AEs. Three subjects experienced SAEs from which 2 were assessed as related to study drug (ALT/AST elevation and pneumonitis). Two subjects experienced 1 AE leading to discontinuation (ALT/AST elevation, TLS, sepsis and GI bleed), and 2 subjects experienced AEs leading to dose reduction (ALT increased and colitis). The most frequent AEs were AST increased, ALT increased, diarrhea and fatigue, rash and headache.

In study 101-11 (Hodgkin lymphoma), exposure to drug ranged from 0.5-13.1 months (median 3.3 months). Five subjects (20%) had a dose reduction, and seven (28%) had a dose escalation. Twenty-four subjects (96%) reported at least 1 AE; the most common AEs were fatigue, AST increased, pyrexia, vomiting, ALT increased, chills and cough. Eleven subjects (44%) had at least 1 AE grade 3 or higher: hypoxia, dyspnea and ALT/AST elevation. Eight subjects (32%) experienced at least 1 SAE, which included pneumonia, herpes zoster, skin infection and pyrexia. There was 1 death in a subject who developed hypoxia. The subject had discontinued study drug due to disease progression and had been receiving palliative chemotherapy.

### 2.1.7. Clinical Pharmacokinetic and Pharmacodynamic Data

After oral administration, idelalisib appears rapidly in plasma. Mean serum half-life range between 6-9 hours. Idelalisib dosed alone over a range of 17-400 mg exhibit less than dose proportional PK. Idelalisib and its major metabolite (GS-563117) are primarily excreted in feces with elimination via urine considered a minor pathway. No clinically relevant food effect was observed on idelalisib PK, thus idelalisib might be given with or without food. Preliminary data indicate no clinically significant differences in idelalisib PK in subjects with hepatic or renal impairment.

Co-administration of idelalisib resulted in higher midazolam systemic exposures (AUC: 5-fold increase;  $C_{max}$ : 2.3-fold increase), indicating that idelalisib is a moderate inhibitor of CYP3A. Hence, co-administration of CYP3A substrates with idelalisib might result in an increase in their systemic exposures (e.g. antiarrhythmic agents, calcium channel blockers, benzodiazepines, certain HMG-CoA reductase inhibitors, PDE5 inhibitors and warfarin). Particular caution is recommended with drugs that are highly dependent of CYP3A for clearance and for which elevated plasma concentrations are associated with serious and/or life-threatening events (e.g. alfentanil, cyclosporine, sirolimus, tacrolimus, cisapride, pimozide, fentanyl, quinidine, ergotamine, dihydroergotamine, astemizole and terfenadine).

Preliminary data indicate that the co-administration of idelalisib and rifampin, a potent inducer of CYP3A, decreases idelalisib exposures by 25%. Co-administration of potent inducers of CYP3A and idelalisib should be avoided (e.g. rifampin, carbamazepine, phenytoin and St. John's wort).

PD evaluations of idelalisib are consistent with the proposed pharmacological anti-tumor effect. Prior to idelalisib dosing, a high level of constitutive pAKT was detected in CLL subjects. Following 8 and 28 days of dosing with idelalisib BID, constitutive phosphorylation of AKT in cells was reduced to the background levels observed in healthy volunteers.

### 2.1.8. Clinical Efficacy

Idelalisib has shown to be active and well tolerated in a range of B-cell malignancies (Benson 2013; Brown 2013). Idelalisib is highly active as monotherapy in CLL, FL, SLL, LPL, MZL and MCL. Responses to idelalisib are characterized by rapid and durable reductions in lymphadenopathy. Consistently positive results have been demonstrated on a number of endpoints including ORR, DOR and PFS. Idelalisib results thus far support its continued evaluation in subjects with B-cell malignancies. Most of the available clinical efficacy data is based on a dose of 150 mg PO twice daily.

Results from the 101-09 study were recently published (Gopal 2014). In this study, 125 patients with indolent NHL (including 10 patients with WM) who had not had a response to rituximab and an alkylating agent or had had a relapse within 6 months after receipt of those therapies received idelalisib at 150 mg PO BID until disease progression or withdrawal from study. The response rate was 57% with 6% CR rate. The median time to response and DOR were 2 months and 12.5 months, respectively, with a median PFS of 11 months. Based on this study, among the 10 WM patients, 1 PD, 1 SD, 6 MR and 2 PR were observed.

## 2.1.2 Study Disease and Rationale

AL amyloidosis is a disease where monoclonal light chains form fibrils that deposit in soft tissues and organs leading to multi-organ dysfunction (typically of kidneys, heart and nerves). Historically, treatment strategies for multiple myeloma are used for AL amyloidosis, with high dose melphalan and bortezomib playing prominent roles. In approximately 5% of cases, AL amyloidosis is associated with an IgM paraprotein. These patients have a unique presentation and natural history. Because clonal CD20+ lymphoplasmacytic cells are usually responsible for IgM paraproteins, treatment paradigms based on Waldenstrom's macroglobulinemia (WM) may be more appropriate than myeloma-based strategies. We recently conducted a retrospective chart review of prospectively collected data on 95 patients diagnosed with IgM-related AL amyloidosis at the BUMC Amyloidosis Center from 1996 through 2012. Forty-six of 95 patients who underwent treatment were included in the analysis. Of the 46 treated patients, the highest hematologic response rate was observed with HDM/SCT (5/5: 100%), followed by bortezomib (9/11: 82%), rituximab (12/15: 80%), IMiDs (3/4: 75%) and non-transplant alkylating agents (17/27: 63%).

The relapsing nature of this disease typically requires sequential lines of therapy. There are no prospective trials performed in this patient population, and no standard of care has been identified. Each of the commonly used regimens have toxicities that are particularly undesirable in amyloid patients. For instance, steroids cause worsening fluid retention and volume status problems in patients already struggling with hypoalbuminemia, heart failure and renal insufficiency. Bortezomib can exaggerate peripheral neuropathy which is very common in AL patients. An effective, steroid-free regimen that does not cause neuropathy would be a major step forward for this field.

Idelalisib, an oral inhibitor of the delta isoform of phosphatidylinositol-3-kinase (PI3K), has been shown to be active and well tolerated in patients with relapsed/refractory non-Hodgkin lymphoma including chronic lymphocytic lymphoma, and lymphoplasmacytic lymphoma with or without Waldenström's macroglobulinemia (WM). The side effect profile of idelalisib merges well with the known predisposition to toxicity of amyloidosis patient. The response rates reported for idelalisib in WM compare favorably with the response rates for IgM-associated AL patients reported in retrospective series. Response rates are likely most favorable in patients with *MYD88L265P* or *CXCR4WHIM mutations*

## 3. PARTICIPANT SELECTION

### 3.1.1 Inclusion Criteria

Participants must meet the following criteria on screening examination to be eligible to participate in the study:

- 3.1.1** IgM paraprotein identified on serum immunofixation electrophoresis OR light chain-restricted CD20+ lymphoplasmacytic population on biopsy of bone marrow or lymph node (identified by H&E/immunohistochemistry or flow cytometry) OR positive myeloid differentiation primary response gene 88 (MYD88-L265P) OR *CXCR4WHIM* mutation on submitted samples
- 3.1.2** Biopsy-proven, relapsed or refractory AL amyloidosis
- 3.1.3** Age  $\geq$  18 years
- 3.1.4** ECOG performance status  $\leq$  2 (see Appendix A.)
- 3.1.5** Difference between serum free light chains (FLC) of  $>30$  mg/L or quantifiable IgM paraprotein  $>0.5$  g/L
- 3.1.6** Participants must have normal organ and marrow function as defined below:

- Absolute neutrophil count  $\geq 1,000/\text{mm}^3$
- Platelets  $\geq 50,000/\text{mm}^3$

**3.1.7** Ability to understand and the willingness to sign a written informed consent document.

### **3.1.2 Exclusion Criteria**

Participants who exhibit any of the following conditions at screening will not be eligible for admission into the study:

- 3.2.1** Previous treatment with idelalisib
- 3.2.2** GFR  $<15 \text{ ml/min}$
- 3.2.3** Cardiac biomarker Stage III disease as determined by BNP  $>100 \text{ pg/mL}$  and Troponin-I  $>0.1 \text{ ng/mL}$  (Girnius 2014)
- 3.2.4** ALT/AST values  $>2.5 \times \text{ULN}$ , Bilirubin  $>1.5 \times \text{ULN}$
- 3.2.5** CNS malignancy or other active malignancy
- 3.2.6** Lactating or pregnant women
- 3.2.7** Exposure to another investigational drug within 4 weeks prior to start of study treatment
- 3.2.8** Ongoing alcohol or drug addiction as determined by investigator
- 3.2.9** Amyloid-directed therapy within the past 28 days
- 3.2.10** History of Human Immunodeficiency Virus (HIV), active Hepatitis B Virus (HBV) (assessed by positive Hep B PCR or HepB Surface Antigen), and/or Hepatitis C Virus (HCV) infection
- 3.2.11** t(11,14) translocation identified on bone marrow cytogenetics or by FISH
- 3.2.12** Known lytic bone lesions
- 3.2.13** Positive CMV PCR
- 3.2.14** Previously untreated AL amyloidosis (newly diagnosed)
- 3.2.15** Unwilling or unable to comply with the protocol

## **4. TREATMENT PLAN**

Treatment will be administered on an outpatient basis. Expected toxicities and potential risks as well as dose modifications for idelalisib are described in Section 6 (Expected Toxicities and Dosing Delays/Dose Modification). No investigational or commercial agents or therapies other than those described below may be administered with the intent to treat the participant's malignancy.

### **4.1.1 Agent Administration**

#### **4.1.1 Idelalisib**

Idelalisib will be administered orally at a dose of 100 mg (one tablet) twice daily. At 3 month visit, if the patient has no toxicities grade 2 or greater that are attributable to idelalisib, dose escalation to 150 mg PO BID is allowed at investigator discretion. Participants will be treated until progression, unacceptable toxicity, or decision to withdraw from the trial. Dose reductions due to toxicity will be permitted, according to dose modification instructions (Section 5).

The study drug idelalisib will be self-administered, and participants will be instructed to write in a diary daily, documenting that the drug was taken. Participants will be instructed to take the study drug at approximately the same time each day. If a dose is missed, it can be taken up to 6 hours after the scheduled time with a return to the normal schedule the following day. If it has been greater than 6 hours, the dose should not be taken and the patient should take the next dose at the scheduled time the next day. The missed dose will not be made up and must be returned to the site at the next scheduled visit; this must be documented in the study diary. Furthermore, they will be instructed to call the PI or research nurse if vomiting occurs. If the pills are vomited a replacement dose should not be taken that day. All dosages prescribed and dispensed to the participant, and all dose changes during the study must be recorded.

Drug accountability will be done at each study visit; unused drug and diaries will be collected from the participant, unused drug will be counted and returned to the pharmacy to be destroyed. A new prescription for either one cycle or three cycles, will be filled by the participant.

Medication labels will comply with US legal requirements and be printed in English. The storage conditions for study drug will be described on the medication label.

Idelalisib will be provided by Gilead Sciences, Inc. Idelalisib is formulated as tablets for oral administration and will be available for this study in 150-mg tablets or 100-mg tablets.

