#### 6.1.2 Idelalisib Package, Storage and Handling

Idelalisib tablets are packaged in white, high-density polyethylene bottles with a polyester fiber coil and are closed by a polypropylene, child resistant induction-sealed cap. Bottles contain 60 tablets.

Measures that minimize drug contact with the body should always be considered during handling, preparation and disposal procedures. Any unused drug should be disposed of in accordance with local requirements.

Idelalisib tablets should be stored at a controlled room temperature between 20-30°C (68-86°F), with excursions permitted from 15°C (59°F) to 30°C (86°F). Brief excursion (less than 1 week) to temperatures as low as -10°C or as high as 40°C will not adversely affect the drug.

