#### 6.1.4 Idelalisib Administration

Idelalisib should be self-administered daily by the participant and should be taken at approximately the same time each day. Idelalisib should be administered orally twice daily with 8 ounces (approximately 240 mL) of water (avoid GRAPEFRUIT JUICE due to CYP450 3A4 inhibition). The tablets should be swallowed intact and participants should not attempt to dissolve tablets in water. If a dose is missed, it can be taken up to 6 hours after the scheduled time with a return to the normal schedule the following day. If it has been greater than 6 hours, the dose should not be taken and the participant should take the next dose at the scheduled time the next day. The missed dose will not be made up and must be returned to the site at the next scheduled visit.

Dietary habits around the time of idelalisib intake should be as consistent as possible throughout the study. If the pills are vomited this should be noted on the diary, but a replacement dose should not be taken that day. A study diary will be used to aid with study drug administration compliance.

At each study visit, enough idelalisib will be dispensed until the next cycle. For visits occurring monthly, one cycle worth of pills will be dispensed. For visits occurring every 3 months, three cycles' worth of pills will be dispensed.

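### The missed-dose rule for twice-daily idelalisib names the next day's dose, so a morning dose missed by more than 6 hours literally cancels that evening's dose as well

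*Combined protocol and SAP*

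**What the plan says.** Section 4.1.1 (Idelalisib) sets the regimen: "Idelalisib will be administered orally at a dose of 100 mg (one tablet) twice daily". Escalation to 150 mg twice daily is allowed at the 3-month visit.

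The same section then gives two rules for a late dose. Up to 6 hours late, the dose may still be taken. If it is later than that, it is skipped, and "the patient should take the next dose at the scheduled time the next day". A skipped tablet is not made up; it is returned at the next visit and recorded in the diary.

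Section 6.1.4 (Idelalisib Administration) restates the frequency, "Idelalisib should be administered orally twice daily with 8 ounces", and repeats the rule for a dose more than 6 hours late: "the dose should not be taken and the participant should take the next dose at the scheduled time the next day".

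Neither section distinguishes a morning from an evening dose, and neither says that the same evening's dose is still due after a missed morning dose. Section 5 deals with interruptions for toxicity, not with doses the patient misses.

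**The concern.** On a twice-daily schedule, the dose that follows a missed morning dose is due the same evening. The rule puts it on the next day. A patient who follows the text therefore omits two doses where the schedule requires only one to be lost, and takes no drug on that calendar day.

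The drug is self-administered by outpatients. Section 4.1.1 tells them to call the site if they vomit, but gives no such instruction for a missed dose, so the written rule may be acted on without anyone being asked.

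There is also a small bookkeeping consequence. Diaries and unused tablets are checked at each visit (section 4.1.1), and inability or unwillingness to comply with the oral regimen is a reason to stop treatment (section 4.1.3). As written, it is unclear whether the omitted evening tablet counts as a second missed dose or as compliance with the protocol.

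What is at stake is a correct dosing instruction. The primary endpoint and the two-stage decision rule are not affected.

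**Working it through.** The plan gives no figure to reproduce here. The check is a reading of the rule against a dose timeline.

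**Inputs**

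- Dose: 100 mg twice daily, 200 mg per day (section 4.1.1).
- Rule for a dose more than 6 hours late: skip it; next dose the next day (sections 4.1.1 and 6.1.4).
- Half-life: 6 to 9 hours (section 2.1.7).
- Assumed: doses 12 hours apart, for example 08:00 and 20:00. The document gives no clock times.
- Assumed: a cycle of 28 days (56 doses) or 30 days (60 doses). Cycle length is not stated. The 30-day figure matches one bottle: "Bottles contain 60 tablets" (section 6.1.2).

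**Timeline for one missed dose**

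| Missed dose | Rule applied | Next dose taken | Doses lost | Gap between doses taken |
|---|---|---|---|---|
| 08:00 | as written | 08:00 next day | 2 | 12 + 24 = 36 h |
| 08:00 | next scheduled dose | 20:00 same day | 1 | 12 + 12 = 24 h |
| 20:00 | as written | 08:00 next day | 1 | 12 + 12 = 24 h |

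The rule fails only for the morning dose.

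**Dose taken that day after a missed morning dose**

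- As written: 0 mg of 200 mg.
- Corrected: 100 mg of 200 mg.
- After escalation to 150 mg twice daily: 0 mg instead of 150 mg, of 2 × 150 = 300 mg.

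**Gap in half-lives** (gap ÷ half-life)

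- As written: 36/9 = 4.0 to 36/6 = 6.0.
- Corrected: 24/9 = 2.7 to 24/6 = 4.0.

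**Share of a cycle's doses taken, with one missed morning dose**

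- 28 days: 54/56 = 96.4% as written, 55/56 = 98.2% corrected. Difference 1/56 = 1.8 percentage points.
- 30 days: 58/60 = 96.7% as written, 59/60 = 98.3% corrected. Difference 1/60 = 1.7 percentage points.

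**The case against.** **The intent is plain.** Both sections prescribe two doses a day and then speak of one missed dose in the singular. No sentence tells the patient to omit the evening tablet; it drops out only through the words placing the next dose on the following day. A reader who reconciles the two would take it. It is fair to infer that losing two doses was not intended. That is a reason to correct the sentence, but it does not change what the sentence says. Nor does the protocol offer any reason for a deliberate precaution, which would in any case make little sense for morning doses only.

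**The effect is very small.** This stands. The excess is one tablet and 12 hours per event, since a 24-hour gap occurs even under the corrected rule. The plan tolerates much longer holds for toxicity, with discontinuation only at about 28 days. Pill counts and diaries should show an extra skipped dose, though only after it has happened.

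**What patients were actually told is not known.** This also stands. The diary text is not in the document, and section 6.1.3 says the drug is shipped with standard commercial labelling, which is not shown. The defect is established for sections 4.1.1 and 6.1.4 only.

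**The neighbouring sentence is loose too.** For a dose up to 6 hours late, the normal schedule is said to resume the following day, which also reads like a once-daily rule. That is so, but it does not weaken the point about doses more than 6 hours late.

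**Conclusion.** The rule is wrong as written in both sections. Followed literally, a morning dose missed by more than 6 hours costs two doses instead of one. The zero-dose day follows from the text alone. The 36-hour versus 24-hour gap rests on assumed 12-hour spacing, and the loss of 1.7 to 1.8 percentage points of a cycle's doses rests on an assumed cycle of 30 or 28 days with one such event. The frequency of such events cannot be estimated from the document.

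This is a minor correction to an operational instruction. It has no bearing on the sample size or the decision rule, and no effect on the response rate is claimed.

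**What to change.** In sections 4.1.1 and 6.1.4, replace the instruction for a dose more than 6 hours late with: *skip the missed dose and take the next scheduled dose at its usual time*. Make the same change in the diary instructions if they carry the sentence. The adjoining rule for a dose up to 6 hours late could be tidied in the same edit, so that it returns the patient to schedule at the next scheduled dose.

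The cost is a few words in two sections and possibly the diary, which can go into the next amendment. Design, sample size and analysis are unchanged.
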